### 14.2. Estimand

Consistent with the International Conference on Harmonisation (ICH) E9 (R1) addendum on estimands and sensitivity analysis in clinical trials to the guideline on statistical principles for clinical trials (FDA 2021), the definition of the attributes of the primary estimand of this study is provided in this section.

The primary estimand of the study is to assess the difference in severity of pruritus in subjects with cholestatic pruritus due to PBC or PSC treated with EP547 or placebo, as measured by change in weekly average WI-NRS after 6 weeks of randomized treatment, regardless of treatment discontinuation and use of prohibited and/or rescue medications.

The population targeted by the scientific question is defined via the inclusion and exclusion criteria as part of the protocol. A key aspect of eligibility is that subjects must have moderate-to-severe pruritus at baseline, as defined as a mean daily WI-NRS score of at least 4.

The primary endpoint to be obtained for each subject in this study to address the scientific question is the mean weekly WI-NRS score at Week 6.

Premature discontinuation from study drug and use of prohibited and/or rescue medications are the primary potential intercurrent events that could occur. The treatment policy strategy is used for the primary estimand, consistent with the intent-to-treat principle.

### **14.3. Endpoints**

#### **14.3.1. Primary Efficacy Endpoint**

The primary efficacy endpoint is the change from baseline in WI-NRS at Week 6.

[figure not shown]
#### **14.3.2. Secondary Efficacy Endpoints**

The secondary efficacy endpoints are:

- Change from baseline in 5-D Itch Scale
- The proportion of subjects with improvement in pruritus as defined by PGI-C
- The proportion of subjects with improvement in pruritus severity from baseline as defined by change in PGI-S
- The proportion of subjects with a reduction in WI-NRS  $\geq 2$  from baseline
- The proportion of subjects with a reduction in WI-NRS  $\geq 3$  from baseline
- The proportion of subjects with a reduction in WI-NRS  $\geq 4$  from baseline
- The proportion of subjects with WI-NRS  $< 4$

#### **14.3.3. Exploratory Endpoints**

Exploratory endpoints include:

### **14.4. Sample Size Considerations**

Assuming a standard deviation of 2.5 points, a sample size of 26 subjects per treatment group provides approximately █% power to detect a difference of █ EP547 and placebo with respect to the change in weekly mean of the daily WI-NRS score based on a 2-sided, 2-sample comparison of means at the 5% significance level. With an anticipated early withdrawal rate of approximately 10%, the planned enrollment of 29 subjects per treatment group will ensure that at least 26 subjects complete the 6 weeks of double-blind treatment.

### **14.5. Demographic and Baseline Characteristics**

Demographic data and baseline characteristics for the FAS, PP, and Safety Analysis Sets will be summarized by treatment group and overall using descriptive statistics.

### **14.6. Subject Disposition**

Disposition of subjects will be summarized by treatment group and overall. Completion status and reasons for discontinuation will also be summarized.

The number and percentage of subjects in each analysis set will be summarized.

#### **14.7. Study Drug Usage and Compliance**

Compliance rate during each treatment period will be computed for each subject and will be summarized for the Safety Analysis Set using summary statistics by treatment group and overall.

Duration of treatment will also be summarized by treatment group for the Safety Analysis Set.

#### **14.8. Efficacy and Pharmacodynamic Analysis**

Efficacy and PD analyses will be based on the FAS. The primary and secondary endpoint analyses will also be repeated in the PP Set as supportive analyses.

All efficacy and PD endpoints will be further evaluated during the Open-Label Extension Period. Summaries of change over time will evaluate both change from baseline (Visit 2 [Day 1]) and change from the initiation of the Open-Label Extension Period (Visit 6 [Week 6]).

For WI-NRS, a weekly score will be determined based on the average of all available daily scores of the week. The average WI-NRS score using the daily values from the week before the first dose of study drug will serve as the baseline score. For any given week, if more than 3 daily scores are missing, the weekly score is considered missing.

All changes from baseline endpoints are defined as absolute change. For select endpoints, percent change from baseline by week will also be summarized.

##### **14.8.1. Analysis of the Primary Endpoint: Change from Baseline in Worst Itch Numeric Rating Scale (WI-NRS) at Week 6**

WI-NRS data will be analyzed using a mixed effects model for repeated measures (MMRM) based on the data from all visits up to Visit 6 (Week 6). The model will include treatment, type of cholestatic disease (PBC, PSC), week, and treatment by week interaction as fixed effects, and baseline WI-NRS score as a covariate. The treatment effect will be the contrast between EP547 and placebo least-squares (LS) means. The LS means, treatment effect estimate, 95% confidence interval, and p-value will be presented. Testing of hypothesis is 2-sided at a 5% type I error level.

##### **14.8.2. Analysis of Secondary and Pharmacodynamic Endpoints**

All efficacy and PD endpoints described in [Sections 14.3.2](#) and [14.3.3](#) will be summarized. Endpoints that are defined as continuous variables will be analyzed using a similar model as described for the primary efficacy endpoint if they are collected at multiple post-baseline visits; otherwise, they will be analyzed using analysis of covariance (ANCOVA) adjusted for randomization strata and baseline measurements of the response parameter of interest. Other endpoints defined as response proportions will be analyzed using a Cochran-Mantel-Haenszel test stratified by randomization strata.

Specifically for WI-NRS, data summaries will present scores, change from baseline, and response proportions by week. Percent change from baseline by week will also be summarized.

### **14.8.3. Primary and Sensitivity Analyses to Address Missing Data in the Primary Analysis**

The primary analysis of the primary endpoint of change from baseline in WI-NRS will include all observed data (weekly WI-NRS scores considered non-missing) with no data imputations, under the assumption of missing at random (MAR).

As a sensitivity analysis, the primary endpoint will also be analyzed with multiple imputation procedures (Rubin 1987). The SAP will provide full detail of the methodologies that will be used.

### **14.9. Safety Analysis**

The Safety Analysis Set will be used for the summaries of the safety data according to the treatment received. Safety data will be summarized separately for the Double-Blind Treatment Period and Open-Label Extension Period by randomized Double-Blind treatment received.

The safety and tolerability of EP547 will be assessed by comparing the frequency, causality, and severity of AEs, as well as treatment discontinuations due to AEs. AEs will be coded using the MedDRA by System Organ Class and preferred term. AEs that begin after the first administration of study drug, or existing AEs that worsen after the first dose of study drug, are considered TEAEs. All AE summaries will include TEAEs, and all AEs will be presented in listings.

The World Health Organization (WHO) DRUG Dictionary will be used to categorize verbatim descriptions of non-study drug into the Anatomic Therapeutic Chemistry (ATC) classification system. Changes in vital signs, standard 12-lead ECGs, laboratory evaluations, and disease-specific assessments (Partial Mayo Score for subjects with UC and CDAI for subjects with CD) will be summarized by treatment group.

### **14.10. Pharmacokinetic Analysis**

A descriptive summary of observed plasma concentrations of EP547 will be displayed by time and by treatment group. The plasma concentrations will be analyzed in the PK Set.

### **14.11. Subgroup Analyses**

The primary efficacy endpoint and selected secondary efficacy endpoints will be analyzed based on age, gender, race/ethnicity, cholestatic liver disease type (PBC or PSC), presence of comorbidities (ie, IBD, CD, and/or UC), OCA use at baseline (yes or no), or other demographic/baseline characteristics, as appropriate. Additional details will be provided in the SAP.

### **14.12. Multiple Comparison/Multiplicity**

This is the first study to explore the efficacy of EP547 for more than 7 days. The familywise error rate will be controlled for the primary efficacy endpoint at  $\alpha = 5\%$ . All other efficacy variables will be tested at the 0.05 level of significance without multiplicity adjustment.

### **14.13. Planned Interim, Primary, and Final Analysis**

To address business needs, an interim analysis may be conducted after approximately 50% of randomized subjects have completed 4 weeks of randomized treatment. Only a limited number of study team members and senior management stakeholders comprising the internal DRT would review the results of the interim analysis of unblinded data from the Double-Blind Treatment Period. The interim analysis would evaluate the effect of EP547 on WI-NRS, select secondary endpoints, and safety.

Additional details about the interim analysis, if applicable, will be provided in the SAP, which is to be finalized before the database lock and unblinding of the study data, as applicable. The SAP will be amended if emerging data from the completed interim analysis leads to substantial change in the study protocol that has significant impact on the statistical analyses.

The primary analysis will be conducted after the last subject randomized has completed the Double-Blind Treatment Period to determine whether the primary efficacy endpoint of change from baseline in WI-NRS at Week 6 is statistically significant. Details regarding the primary analysis procedures, including database lock and unblinding procedures, will be finalized prior to analysis.

The final analysis will be conducted when all randomized subjects have completed the Open-Label Extension Period or are discontinued from the study, and the final database is locked.

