#### **9.3.2. Blinding**

The Sponsor, Medical Monitor, Contract Research Organization (CRO) staff, Investigators, site staff, and subjects will be blinded to subject's assigned treatment during the Double-Blind Treatment Period of the study until the database is locked except for CRO or vendor staff involved in the analysis of PK samples or safety reporting to regulatory agencies.

To address business needs, a limited number of study team members and senior stakeholders comprising the internal Data Review Team (DRT) may conduct and review an interim analysis of unblinded data from the Double-Blind Treatment Period ([Section 14.13](#)). The rest of the central study and project team members will remain blinded.

Treatment with 100 mg doses of EP547 during the Open-Label Extension Period will be conducted in an unblinded manner.

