# 4.2 Analysis Sets

The analysis sets are defined as follows for the Double-Blind Treatment Period:

• Full Analysis Set: All subjects who are randomized and take at least 1 dose of randomized study drug will be included in the Full Analysis Set. Subjects in the Full Analysis Set will be analyzed according to randomized treatment assignment. If a subject is incorrectly stratified (i.e., randomized according to an incorrect stratification), the subject will be analyzed under the randomized treatment for the stratum recorded in the IWRS. All efficacy and PD analyses will be based on the Full Analysis Set.

- Per Protocol Set: The Per Protocol Set is a subset of the Full Analysis Set containing subjects who meet study eligibility requirements and have no protocol deviations that might impact the assessment of efficacy measurements. Subjects will be analyzed according to randomized treatment assignment. The Per Protocol Set will be used for sensitivity analyses relating to efficacy and PD. Protocol deviations that qualify for exclusion from the Per Protocol Set include:
  - Deviations of inclusion/exclusion criteria
  - Non-permitted concomitant medications that may meaningfully impact efficacy outcomes (e.g., receipt of prohibited and/or a rescue medication qualifying as an intercurrent event)
  - Meaningful dosing and/or randomization error(s)
  - Any other important protocol deviation deemed by the Sponsor to warrant exclusion from the Per Protocol set

Any protocol deviations that govern exclusion from the Per Protocol Set will be determined prior to database lock and primary analysis.

- Safety Analysis Set: All subjects who are randomized and take at least 1 dose of randomized study drug will be included in the Safety Analysis Set. Safety analyses will be based upon treatment actually received.
- PK Set: All subjects who receive at least 1 dose of EP547 and provide adequate blood samples for bioanalysis will be included in the PK Set.

Data summaries to be presented on both the Safety Analysis Set and the Full Analysis Set will only be produced on both analysis sets if there is a difference in the population groups.

An Open-Label Extension Analysis Set will be determined as all subjects who complete the Double-Blind Treatment Period and receive at least one dose of study drug in the Open-Label Extension Period and will be used to summarize all available data collected in both the Double-Blind and Open-Label Extension Periods.

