#### 4.3.2 Protocol Deviations

Important Protocol Deviations (IPDs) will be summarized by treatment group and over all subjects combined for the Full Analysis Set. Important Protocol Deviations are identified by the Sponsor and are defined in the ICH guideline *Structure and Content of Clinical Study Reports – Questions and Answers (E3[R1], 2013)* as a subset of protocol deviations that might significantly affect the completeness, accuracy, and/or reliability of the study data or that might significantly affect a subject's rights, safety, or well-being.

All IPDs will be determined and appropriately categorized prior to database lock and prior to breaking the blind of the treatment group assignments. The number and percentage of subjects with any IPDs as well as the number and percentage of subjects with IPDs within each category will be presented. A listing of important protocol deviations will be provided.

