# 4.4.3 Primary Efficacy Endpoint Analysis Methods

The primary estimand is the difference in means between treatment groups in the weekly WI-NRS score at Week 6 for all subjects in the Full Analysis Set. The treatment policy strategy for addressing intercurrent events will be used for the primary estimand; data collected following use of prohibited and/or rescue medications or for subjects who prematurely discontinue from study drug use will be reported in the analysis. The WI-NRS data will be analyzed using a mixed effects model for repeated measures (MMRM) based on the data from weekly scores up to Visit 6 (Week 6) in the Double-Blind Treatment Period. The model will include treatment, type of cholestatic disease (PBC, PSC), week, and treatment by week interaction as fixed effects, and the baseline WI-NRS weekly score as a covariate. The unstructured covariance model will be used. In the event the computational algorithm fails to converge, the following structures will executed: heterogeneous Toeplitz, Toeplitz, heterogeneous Autoregressive [AR(1)], AR(1), heterogeneous compound symmetry (CS), and CS. The covariance structure converging to the best fit, as determined by Akaike's information criterion (AIC), will be used. The Kenward-Roger approximation will be used to calculate the denominator degrees of freedom for the test of fixed effects. The null hypothesis to be tested is that there is no difference between EP547 and Placebo:

$$H_0$$
:  $\mu_A = \mu_B$ ;

Where  $\mu_A$  and  $\mu_B$  represent the mean values for EP547 and Placebo, respectively. The alternate hypothesis to be tested is that the treatment group means differ:

$$H_1$$
:  $\mu_A \neq \mu_B$ ;

Testing of the hypothesis is 2-sided at a 5% type I error level. Estimates of least-square (LS) means, standard error, and 95% CIs will be presented by treatment group. In addition, the LS mean difference (LSMD) of the comparison between EP547 and placebo, the standard error of the difference, and 95% CI of the difference will be presented.

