# 4.4.5 Exploratory Endpoint Analysis Methods

# 4.4.6 Sensitivity Analysis of Efficacy Endpoints

Sensitivity analyses of the primary endpoint will be conducted to better assess the impact of intercurrent events on the efficacy conclusions. The intercurrent events of interest include receipt of prohibited and/or rescue medications while on study and early withdrawal of study drug. The treatment policy strategy will be used for the primary estimand.

The while on treatment strategy will be used as a sensitivity analysis to further explore the intercurrent event of prohibited and/or rescue medication usage. The difference in means between treatment groups in the weekly WI-NRS score at the last visit prior to receipt of prohibited and/or rescue medications (or the last derived weekly WI-NRS score, for those who never require prohibited and/or rescue medication) will be presented during the Double-Blind Treatment Period. For those subjects that receive a prohibited and/or rescue medication, any WI-NRS scores reported after the receipt of medication will be excluded from the analysis.

Determination of intercurrent events based on use of a prohibited and/or rescue medication will be based on review of the Concomitant Medication eCRF. Before study unblinding, the sponsor will review all reported concomitant medications, including onstudy changes to background medications, to determine which qualify as an intercurrent event for prohibited or rescue medication usage. This external assessment will be documented in the study files and integrated into the sensitivity analysis.

The analysis of the primary efficacy endpoint will be analyzed for the Full Analysis Set using multiple imputations (MI) assuming data missing at Week 6 to be missing at random (MAR) (Section 4.4.7.2), and for the Per Protocol Set using observed data.

Treatment group comparisons will use the methodology described in Section 4.4.3 for sensitivity analysis of the primary endpoint.

Secondary and PD endpoint analyses during the Double-Blind Treatment Period will be repeated for the Per Protocol Set as supportive analyses.

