# 4.4.7.3 Planned Interim, Primary, and Final Analyses and Data Monitoring

To address business needs, an interim analysis may be conducted after approximately 50% of randomized subjects have completed 4 weeks of randomized treatment. Only a limited number of study team members and senior management stakeholders comprising the internal DRT would review the results of the interim analysis of unblinded data from the Double-Blind Treatment Period. The interim analysis would evaluate the effect of EP547 on WI-NRS, select secondary endpoints, and safety.

The primary analysis will be conducted after the last subject randomized has completed the Double-Blind Treatment Period to determine whether the primary efficacy endpoint of change from baseline in WI-NRS at Week 6 is statistically significant. Details regarding the primary analysis procedures, including database lock and unblinding procedures, will be finalized prior to analysis.

The final analysis will be conducted when all randomized subjects have completed the Open-Label Extension Period or are discontinued from the study, and the final database is locked.

The Data Monitoring Committee (DMC) is an independent group of external experts who will review safety data during the conduct of the study, as outlined in the DMC charter. The DMC will make a determination of relatedness for all AEs with CTCAE Grade 3 or higher. The DMC will also meet on an ad hoc basis when at least 3 AEs of CTCAE Grade 3 or higher have accrued or when there has been a single CTCAE Grade 4 or higher. Based on review of the data, the DMC will provide recommendations to the Sponsor on whether the nature, frequency, and/or severity of AEs associated with study drug warrant modification to the study protocol, suspension of dosing, or study termination.

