# 4.4.7.5 *Multiple Comparisons/Multiplicity*

This is the first study to explore the efficacy of EP547 for more than 7 days. The familywise error rate will be controlled for the primary efficacy endpoint at an alpha of 5%. All other efficacy endpoints will be tested at the 0.05 level of significance without multiplicity adjustment.

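### Does the optional unblinded sponsor interim put the 5% level of the primary WI-NRS test at risk?

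*Protocol*

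**What the plan says.** Protocol 9.3.2 and SAP 3.3.4 allow an unblinded look inside the sponsor: "a limited number of study team members and senior stakeholders comprising the internal Data Review Team (DRT) may conduct and review an interim analysis". Everyone else on the central study and project team stays blinded. Protocol 14.13 and SAP 4.4.7.3 place the look after about 50% of randomized subjects have completed 4 weeks, make it optional, and give business needs as the reason. Its content is stated in SAP 4.4.7.3: "The interim analysis would evaluate the effect of EP547 on WI-NRS, select secondary endpoints, and safety".

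Protocol 14.13 leaves further interim details to the SAP and provides for a revised SAP in one event: "if emerging data from the completed interim analysis leads to substantial change in the study protocol that has significant impact on the statistical analyses". SAP 4.4.7.3 repeats the interim paragraph and adds no boundary, adaptation rule or list of permitted changes.

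On error control, SAP 4.4.7.5 states that "The familywise error rate will be controlled for the primary efficacy endpoint at an alpha of 5" percent, and SAP 4.4.3 adds: "Testing of the hypothesis is 2-sided at a 5% type I error level". Both documents give the decision on significance to the primary analysis, held after the last randomized subject completes the double-blind period. SAP section 1 requires the SAP to be final before data analysis, treatment unblinding and database lock, and requires departures from it to be documented in the study report.

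Three sponsor decisions are meant to be made blind or before lock:
- Important deviations are fixed "prior to database lock and prior to breaking the blind of the treatment group assignments" (SAP 4.3.2).
- For intercurrent events, "Before study unblinding, the sponsor will review all reported concomitant medications" (SAP 4.4.6).
- Per Protocol exclusions, set before database lock and primary analysis, include "Any other important protocol deviation deemed by the Sponsor to warrant exclusion from the Per Protocol set" (SAP 4.2).

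**The concern.** People with authority over the trial could see the treatment effect on the primary measure halfway through. The protocol itself mentions a substantial change arising from what they see. It does not say that only safety data may prompt one, so an efficacy-driven change to sample size, population or primary analysis is not ruled out. Both documents nevertheless promise 5% for the primary endpoint, and neither names a method that would keep it after such a change. If the promise failed, a positive proof-of-concept result would be somewhat less reliable than its p-value suggests.

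A smaller worry sits beside this. The intercurrent-event review and the Per Protocol exclusions rely on blinding, but no sentence keeps team members who saw the interim results out of them.

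**Working it through.** **Inputs from the documents.** Two-sided 5% (critical value 1.96), 26 evaluable and 29 enrolled per arm, 10% withdrawal, 1:1 allocation, and an interim at about 50% of subjects. The enrollment figure reproduces: 26/0.9 = 28.9, so 29 per arm.

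**Assumptions, not in the documents.** The information fraction t for Week 6 is taken as 0.5, with 0.4 and 0.6 as a range. The final test is left unadjusted after any change.

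**1. The plan as written.** Let z1 and z2 be the standardized results before and after the interim, and r the ratio of stage-2 to stage-1 size. The final statistic is

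Z = (z1 + √r · z2)/√(1 + r).

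With r fixed in advance at (1 − t)/t, which is 1 at t = 0.5, Z is standard normal under the null and P(|Z| > 1.96) = 5.0%. A look with no claim and no change does not alter this. Nor does a futility stop raise it. For example, if the trial stops whenever z1 < 0, only the outcomes with z1 > 0 can still reject, and by symmetry these are half the total, 2.5%.

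**2. Most damaging sample size increase.** Suppose the total may grow to m times plan, so r may lie anywhere between 1 and m/0.5 − 1. For every z1, choose the r that maximizes the chance of rejection, then average over z1 ~ N(0,1):

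| Cap m | Per arm | Largest r | Error, t = 0.5 | t = 0.4 | t = 0.6 |
|---|---|---|---|---|---|
| 1.25 | about 36 | 1.5 | 5.47% | 5.38% | 5.56% |
| 1.5 | about 44 | 2 | 5.79% | 5.65% | 5.94% |
| 2 | 58 | 3 | 6.20% | 5.99% | 6.42% |

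A simulation of 2 million paths at t = 0.5 gave 5.82% and 6.24% for the caps 1.5 and 2, with 5.03% for the look alone in the same paths.

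**3. Where the excess comes from.** At t = 0.5, enlarging the trial helps a false rejection only when |z1| < 1.96/√2 = 1.386, that is, after a weak interim. The figures above also count enlargement when the interim favours placebo. If the sponsor enlarges only when it favours EP547, half the excess goes:
- m = 1.25: 5 + 0.47/2 = 5.2%
- m = 1.5: 5 + 0.79/2 = 5.4%
- m = 2: 5 + 1.20/2 = 5.6%

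**4. A more usual rule.** Suppose the trial is enlarged only when conditional power under the observed trend, in either direction, is 50% to 90%. At t = 0.5, conditional power reaches 50% when |z1|/√0.5 = 1.96, so |z1| = 1.386. The rule therefore acts only outside the region that inflates the error. It gives 4.83%, 4.70% and 4.53% for the three caps.

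**5. The blinded decisions.** The primary analysis uses the treatment policy strategy on the Full Analysis Set (SAP 4.4.3), so data after prohibited or rescue medication stay in. The medication review feeds the while-on-treatment sensitivity analysis and a listing (SAP 4.4.6, 4.5.6.6). The Per Protocol Set is for sensitivity or supportive analyses (SAP 4.4.6, 4.4.7.6). Neither decision can move the primary estimate or its p-value.

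**The case for a change.** The strongest reply is that the design-change scenario is the protocol's own. A business purpose does not forbid a redesign, and a promise to amend the SAP documents a change without controlling its error. An amendment written after unblinding cannot be presumed to be free of the data. The safety remit of the data monitoring committee and the ethics committee approval of amendments do not deal with type I error either.

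Sample size is also not the only route. Restricting the trial at the interim to whichever looked better, all subjects or one disease stratum, and testing without adjustment would give 6.2% to 7.0% for stratum shares from 84% down to 50%. Claiming success at the interim at an unadjusted 5% would give 8.3% at t = 0.5.

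All of this is correct, and the silence is real. But each figure needs an action that the plan does not contain, followed by an analyst who ignores the stated 5% obligation when rewriting the SAP. That obligation carries over to any amended SAP, and the SAP must be final before unblinding, so an efficacy-driven departure would be visible. A method cannot usefully be fixed now for an undefined change that may never occur.

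A flat ban on efficacy-driven changes would also have a price. It gives up redesign in a small proof-of-concept trial, and read literally it could block a futility stop, which does no harm to the error rate. As for recusal, the blinded members of the central team can make the two decisions without a further rule.

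**Conclusion.** No change to the plan is needed. As written, there is an optional internal look, no early claim and one final test, so the two-sided error is 5.0%. What is missing is a policy for a hypothetical amendment. Protocol 14.13 already requires a SAP amendment in that event, and a competent statistician would state there how 5% is preserved.

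The 5.5% to 6.2% range (t = 0.5, caps of 1.25 to 2 times plan) is an adversarial ceiling under assumed re-estimation. It becomes 5.2% to 5.6% if the trial is enlarged only on results favouring EP547, and there is no inflation under a conditional power rule of 50% to 90%. For a phase 2 trial of about 58 subjects, meant to guide a later dose-finding study, an excess of that size does not justify giving up flexibility now.

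The recusal point is a housekeeping matter confined to sensitivity and supportive analyses and a listing. The conclusion rests on the interim staying as described. If efficacy results did prompt a change to the endpoint, population, sample size or primary analysis, the error rate would have to be worked out for that change.
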